1 SYNOPSIS

Name of Sponsor/Company: Aquinox Pharmaceuticals (Canada) Inc.
Name of Product: AQX-1125 Name of Active Ingredient: AQX-1125
Title: A 12-Week, Randomized, Multi-Center, Double-Blind, Placebo-Controlled, Parallel-Group, Phase 2 Trial to Evaluate the Efficacy and Safety of AQX-1125 (200 mg) in Male Subjects with Chronic Prostatitis/Chronic Pelvic Pain Syndrome
Development Phase: 2

Objectives:
 
Primary Objective
 
The primary objective of this study is to evaluate the effect of 12 weeks of treatment with AQX-1125 (200 mg) administered orally once-daily compared to placebo on the change from Baseline (Visit 2) to Week 12 (Visit 4) in maximum daily pelvic pain (mean) in male subjects with non-bacterial chronic prostatitis/chronic pelvic pain syndrome (CP/CPPS) using a standardized 11-point Numerical Rating Scale (NRS) pain score recorded daily by an electronic diary (eDiary).
 
Secondary Objectives
 
The secondary objectives of this study are to evaluate:
 
 • The effects of 12 weeks of treatment with AQX-1125 (200 mg) administered orally once-daily compared to placebo on the change from Baseline (Visit 2) to Week 12 (Visit 4) for each of the following: 
 ○ National Institutes of Health Chronic Prostatitis Symptom Index (NIH-CPSI) pain subscale and all domains total score ○ Male sexual health as measured using the International Index of Erectile Function Questionnaire, Erectile Function Domain (IIEF-EF) ○ Average daily pelvic pain (eDiary), average and maximum pelvic pain (Paper-based NRS, in clinic), using the standardized 11-point NRS ○ 24-hour voiding frequency (eDiary) • Time course of effects: AQX-1125 (200 mg) compared to placebo on the change from Baseline (Visit 2) to Week 6 (Visit 3), Week 12 (Visit 4), and Week 16 (i.e. 4 weeks after end of treatment) for each of the pain and symptom scale endpoints • The overall response to treatment for AQX-1125 (200 mg) compared to placebo as measured by the subject's Global Response Assessment (GRA), Patient's Global Impression of Change scale (PGI-C) and Patient's Global Impression of Severity scale (PGI-S) at Week 12 (Visit 4) • The proportion of subjects with $\geq 30\%$ and $\geq 50\%$ improvement in maximum daily pelvic pain (mean) using the standardized 11-point NRS recorded by the eDiary and the NIH-CPSI pain subscale compared to placebo, at Weeks 6 (Visit 3) and 12 (Visit 4) • Responder analysis: response to treatment defined by any of the following: 
 ○ Decrease in maximum daily pelvic pain from Baseline to Week 12 (eDiary) with no change in the amount or strength of concomitant analgesic medications ○ Decrease in maximum daily pelvic pain from Baseline to Week 12 (eDiary) with a decrease in the amount or strength of concomitant analgesic medications • Discontinuation of study medication due to treatment failure (% meeting treatment failure criteria and time to event) 
Safety Objectives
 
The safety objectives of this study are to evaluate:
 
 • Safety and tolerability of AQX-1125 (200 mg) compared to placebo during the 12-week treatment period • Ocular safety based upon assessment of lenticular opacification using Lens Opacification Classification System (LOCS) III, best corrected visual acuity (BCVA) using the Logarithm of the Minimum Angle of Resolution (LogMAR) chart, intraocular pressure (IOP), corneal staining, and slit lamp examination

Name of Sponsor/Company: Aquinox Pharmaceuticals (Canada) Inc.
Name of Product: AQX-1125 Name of Active Ingredient: AQX-1125

Methodology:
 
In this double-blind, placebo-controlled study, approximately 100 male subjects diagnosed with CP/CPPS will be randomized to either AQX-1125 (200 mg) or placebo in a 1:1 ratio across approximately 30 centers in North America. The study will consist of a screening period of up to 3 weeks, a 12-week treatment period followed by a 4-week Off-Treatment Safety Follow-up period, and an Ophthalmic Safety Follow-up Visit 6 months post last dose, for a total study duration of about 41 weeks. There will also be a follow-up telephone call 3 months after the last dose.
 
At Screening Visit 1, each subject will complete a set of questionnaires, and receive (and be trained to use) an eDiary. Subjects will record their average and maximum daily pelvic pain score, at approximately the same time each day (in the evening prior to the last dose of pain medication), as well as their daily use of analgesic pain medications. Baseline ophthalmic assessments, including lenticular opacification assessment using LOCS III, can be completed as a separate visit any time during the screening period (any time before Visit 2).
 
At Baseline (Visit 2), all subjects will return to the clinic for review of eligibility and to complete the efficacy questionnaires and assessments to establish Baseline values. Average daily pelvic pain scores recorded in the eDiary within the 7 days prior to Baseline (Visit 2) will be part of the study entry criteria. If all entry criteria are met, the subject will be randomized (1:1) to receive a single daily oral dose of 2 tablets for 12 weeks as follows:
 
 • AQX-1125 200 mg dose group: 2 AQX-1125 100 mg tablets; or, • Placebo group: 2 placebo tablets 
All enrolled subjects will record the following in the eDiary (from Screening Visit 1 to Week 16 [Off-Treatment Safety Follow-up Visit]):
 
 • Maximum daily pelvic pain: subjects will assess their maximum pelvic pain for that day on a scale of 0 to 10, with 0 indicating 'no pelvic pain' and 10 indicating 'pelvic pain as bad as you can imagine' • Average daily pelvic pain. Subjects will assess their average pelvic pain for that day on a scale of 0 to 10, with 0 indicating 'no pelvic pain' and 10 indicating 'pelvic pain as bad as you can imagine' • Analgesic medication taken each day • 24-hour voiding frequency: voiding frequency will be measured over a 24-hour period, within a 3-day (72-hours) window before the next scheduled visit (Visit 2, 3, 4 and Off-Treatment Safety Follow-up Visit) 
At Week 6 (Visit 3), and Week 12 (Visit 4), and Week 16 (Off-Treatment Safety Follow-up Visit) during the clinic visit, subjects will complete NIH-CPSI, paper-based 11-point NRS (average and maximum pelvic pain experienced over the last 24 hours), GRA, PHQ-9, PGI-C, IIEF, PGI-S, have vital signs assessed and return unused study drug (Week 6 and 12). Any adverse events (AEs) are to be recorded.
 
Subject compliance with the eDiary will be monitored by trained study site personnel at each study visit.
 
All subjects completing the 12 weeks of treatment (Visit 4) will be considered completers of treatment. Subjects who withdraw from the study during the treatment period should complete an Early Termination Visit. Subjects who discontinue the double-blind treatment for any reason will be encouraged to continue with all subsequent study-related visits and evaluations, with emphasis on obtaining pelvic pain data, analgesic medication data and voiding frequency data to assess efficacy endpoints. Subjects who complete the study or early terminate during the study will be asked to return for the Safety Follow-up Visit 4 weeks after discontinuing study drug, and the Ophthalmic Safety Follow-up Visit 6 months after the last dose. Subjects will also be contacted via telephone for the follow-up telephone call 3 months after their last dose.


Number of Subjects:
 
Approximately 100 male subjects at approximately 30 sites in North America.

Diagnosis and Main Criteria for Inclusion:
 
Inclusion Criteria
 
For inclusion into the screening period subjects must meet the following criteria:

Name of Sponsor/Company: Aquinox Pharmaceuticals (Canada) Inc.

Name of Product: AQX-1125

Name of Active Ingredient: AQX-1125

1. Provide written informed consent and the willingness and ability to comply with all aspects of the study requirements
2. Males, ≥ 18 and ≤ 80 years of age at Screening Visit 1
3. Have pain or discomfort in the pelvic region for at least 3 months in the last 6 months, in the absence of a urinary tract infection or other pelvic/urological cause, and have a physician diagnosis of CP/CPPS (NIH Prostatitis Category III)
4. NIH-CPSI of ≥ 15 on the total score
5. Subjects must agree to use a condom for sexual intercourse from Screening Visit 1 until at least 90 days after the last dose of study drug, unless they have been surgically sterilized (vasectomy) for a minimum of 6 months. True abstinence from sexual intercourse in accordance with the preferred and usual lifestyle of the subject is also acceptable
6. Have an average daily pelvic pain score of ≥ 4 out of 10 on the 11-point NRS pain scale (mean of the average daily pelvic pain score recorded at each of the 7 days prior to Baseline [Visit 2]). A minimum of 5 daily records within 7 days prior to Baseline (Visit 2) must be recorded
7. Must be capable of voiding independently for 30 days prior to screening (to allow completion of 24-hour voiding diary)

Exclusion Criteria

Subjects meeting any of the following criteria are ineligible for trial:

1. Diagnosis of NIH Prostatitis Categories I (acute prostatitis) or II (chronic bacterial) prostatitis
2. Diagnosis of interstitial cystitis/bladder pain syndrome (IC/BPS) with symptoms of pain, pressure, or discomfort perceived to be related to the bladder, and associated lower urinary symptoms for >6 weeks in the absence of infection or other identifiable causes
3. Relief of pelvic pain after voiding or have >15 voids per day
4. Post-void residual volume >150 mL
5. Have had an unresolved (positive bacterial urine culture) urinary tract infection within 8 weeks (inclusive) prior to Screening Visit 1 (subjects can rescreen [up to 1 time] once infection clears)
6. History of previous prostate or bladder intervention (i.e. prostate biopsy, cystoscopy, or indwelling urinary catheter) within 1 month of Screening Visit 1, history of microwave therapy, transurethral resection of the prostate, transurethral radiofrequency thermotherapy, transurethral incision of the prostate, transurethral needle ablation, transurethral laser vaporization of the prostate, Urolift®, Rezum, and other urological interventions (e.g., botulinum toxin) within 6 months of Screening Visit 1
7. Unilateral testicular or scrotal pain as the sole symptom of CP/CPPS
8. Ongoing, symptomatic urethral stricture disease
9. Catastrophizing pain score of ≥ 30 as determined by the Pain Catastrophizing Scale (PCS)
10. Current major depressive disorder (i.e. Patient Health Questionnaire-9 [PHQ-9] score ≥ 10)
11. Neurologic disease or disorder affecting the bladder, ability to void spontaneously, or directly contributing to urinary symptoms (e.g., multiple sclerosis, autonomic neuropathy)
12. Severe, excruciating pain during rectal exam (i.e. an “inability to perform the exam”)
13. History of chronic substance abuse, dependency or abuse of opioids, or other narcotics within the last 2 years
14. Currently receiving, or expect to receive, any of the following prohibited medications or procedures:
 - **Non-steroidal anti-inflammatory drug or other medication (e.g. alpha-blockers) for CP/CPPS, unless on a stable dose for ≥ 30 days prior to Screening Visit 1**
 - **Long-acting opioids:** within 2 weeks prior to Baseline (Visit 2) or expected to take any long-acting opioids at any time during the study

Name of Sponsor/Company: Aquinox Pharmaceuticals (Canada) Inc.
Name of Product: AQX-1125 Name of Active Ingredient: AQX-1125

 • Short-acting opioid or opioid-containing analgesics: more than 10 doses/month, or more than a single dose > 2 days per week, or any short-acting opioid within 3 days prior to randomization • Oral steroid therapy, immunosuppressants / immunomodulators (including daily phosphodiesterase Type 4 inhibitors) within 30 days prior to Screening Visit 1 and throughout the study • Have taken any investigational drug or device within 90 days prior to Screening Visit 1, or have had previous exposure to AQX-1125 
15. Any prior history of pelvic cancer (e.g., colorectal, genitourinary) or treatment (radiation or chemotherapy) thereof
 
16. Major surgery within 3 months prior to Screening Visit 1
 
17. Have any other condition/disease which, in the opinion of the Investigator, could compromise subject safety or interfere with the subject's participation in the study or in the evaluation of the study results. In case of any doubt, the Investigator shall consult the medical monitor.
 
18. Known intolerance to micro-crystalline cellulose (Avicel® PH-102), mannitol or other ingredient of AQX-1125 tablets

Test Product, Dose and Mode of Administration:
 
Two AQX-1125 (activator of the Src homology 2-containing inositol-5'-phosphatase 1 protein) 100 mg tablets will be administered orally once daily with a glass of water, around the same time of day, for 12 weeks. Tablets should be taken with food or eat a light meal no more than 4 hours prior to consumption.

Reference Therapy, Dose and Duration of Administration:
 
Matching placebo is identical in appearance to the test product and contains no active ingredient. Two placebo tablets will be administered orally once daily with a glass of water, around the same time of day, for 12 weeks. Tablets should be taken with food or eat a light meal no more than 4 hours prior to consumption.

Duration of Treatment:
 
Subjects will participate in a 12-week, double-blind treatment phase. After the treatment phase, there will be a 4-week post last dose Safety Follow-up, as well as a 6-month post last dose Ophthalmic Safety Follow-up. There will also be a 3-month post last dose Telephone Call Follow-up.


Variables:
 
Primary Endpoint
 
The primary endpoint is the change from Baseline (Visit 2) to Week 12 (Visit 4) in the maximum daily pelvic pain (mean) using a standardized 11-point NRS pain score recorded daily by an eDiary.
 
Secondary Endpoints
 
The secondary endpoints are:
 
 • The change from Baseline to Week 12 for each of the following: 
 ○ NIH-CPSI pain subscale and all domains total score ○ Male sexual health as measured using the IIEF-EF ○ Mean of average daily pelvic pain scores (eDiary), average and maximum pelvic pain (Paper-based NRS in clinic) ○ 24-hour voiding frequency (eDiary) • Time course of effects: AQX-1125 (200 mg once-daily) compared to placebo on the change from Baseline (Visit 2) to Week 6 (Visit 3), Week 12 (Visit 4), and Week 16 (i.e. 4 weeks after end of treatment) for each of the following: 
 ○ Mean of maximum daily pelvic pain score (eDiary) ○ NIH-CPSI pain subscale and all domains total score

Name of Sponsor/Company: Aquinox Pharmaceuticals (Canada) Inc.

Name of Product: AQX-1125
 
Name of Active Ingredient: AQX-1125


 ○ IIEF-EF ○ Mean of average daily pelvic pain scores (eDiary), average and maximum pelvic pain (Paper-based NRS in clinic) ○ 24-hour voiding frequency (eDiary) ● Response to treatment compared to placebo as measured by the GRA, PGI-C, and PGI-S at Week 12 (Visit 4) ● A $\geq 30\%$ and $\geq 50\%$ improvement in maximum daily pelvic pain (using the 11-point NRS recorded by eDiary and the NIH-CPSI pain subscale) compared to placebo, at Week 6 (Visit 3) and Week 12 (Visit 4) ● Responder analysis: Response to treatment defined by any of the following: 
 ○ Decrease in maximum daily pelvic pain from Baseline to Week 12 (eDiary) with no change in the amount or strength of concomitant analgesic medications ○ Decrease in maximum daily pelvic pain from Baseline to Week 12 (eDiary) with a decrease in the amount or strength of concomitant analgesic medications ● Discontinuation of study medication due to treatment failure (% meeting treatment failure criteria and time to event) 
Safety Endpoints
 
The safety endpoints are:
 
 ● The frequency and severity of AEs will be reported for the treatment phase and will include: 
 ○ Abnormal, clinically significant vital signs, laboratory tests, electrocardiogram (ECG), weight or findings on physical examinations ○ Ophthalmic safety based upon assessment of lenticular opacification using LOCS III, BCVA using the LogMar chart, IOP, corneal staining and slit lamp examination at Baseline, 12 weeks, and 6 months post last dose, and at Early Termination (ET).

Statistical Methods:
 
This study will investigate the comparative treatment effect of AQX-1125 versus placebo in subjects with CP/CPSPS. The statistical analysis will use inferential methods (P values) and estimation (point estimates with confidence intervals) to evaluate the effect of AQX-1125 compared to placebo. This study is powered to demonstrate a statistically significant effect of AQX-1125 versus placebo ($P < 0.05$) in the primary endpoint, if the treatment effect is sufficiently large. If a statistically significant result is not obtained but the estimated effect predicts a statistically significant effect in a larger, subsequent study comparing AQX-1125 to placebo, this study will be considered a success.
 
Sample Size and Power
 
Sample size was calculated using the 2-sample means statement in the POWER procedure in SAS. A sample size of 45 subjects per treatment group will provide 80% power to detect a 1.2-point difference in the change from Baseline maximum pelvic pain score between AQX-1125 and placebo assuming a between-subject standard deviation of 2.0 and a 2-sided 5% significance level.
 
Assuming a 10% rate of discontinuation from study drug, the total number of subjects to be randomized is approximately 100. Subjects who discontinue will be included in the primary analysis, resulting in a slight decrease in power if the discontinuing subjects in the placebo group have no additional change after discontinuation of study drug while the discontinuing subjects in the AQX-1125 group have a loss of efficacy after discontinuing study drug.
 
Analysis
 
Subject pelvic pain as assessed by the 11-point NRS (eDiary) will be summarized at each week during the study. Analyses in the week prior to the Week 6 Visit, Week 12 Visit and Week 16 Visit (Off-Treatment Safety Follow-Up) will be produced with mean, median, standard deviation, and quartiles for both pelvic pain score and the change from baseline in pelvic pain score, using the mean of the maximum observed value from each of the 7

Name of Sponsor/Company: Aquinox Pharmaceuticals (Canada) Inc.
Name of Product: AQX-1125
Name of Active Ingredient: AQX-1125

days prior to each visit (Baseline, Week 6, Week 12 and Week 16). This will be reported for maximum daily pelvic pain score and similarly for average daily pelvic pain score. The proportion of subjects who respond to treatment at Week 6, Week 12 and at Week 16 will be summarized. Use of concomitant analgesic medication will be summarized with the percentage (%) of subjects taking each class of medication (permitted short-acting opioid-containing analgesics and non-opioid containing analgesics: e.g., acetaminophen) and the daily dose (mean, median, standard deviation, and quartiles, using subjects who took any such medication on at least 1 of the 7 days prior to the Baseline, Week 6, Week 12 or Week 16 Visit).
 
Other secondary endpoints will be summarized at Baseline, Week 6, Week 12, and Week 16, including observed values at each timepoint and change from Baseline at post-baseline timepoints, with mean, median, standard deviation, and quartiles for continuous data, and counts and percentages for categorical and binary data.
 
Comparison of AQX-1125 to placebo at Week 12 for the primary efficacy endpoint will use repeated measures analysis of variance to compare change from Baseline in maximum pain score (NRS score) (dependent variable) between treatment arms (AQX-1125 and placebo). Baseline maximum pain score (NRS score) will be included in the model as a covariate. Change from Baseline to Week 6 and Week 12 will be included in the analysis. A P value less than or equal to 0.05 for the change from Baseline at Week 12 will be considered statistically significant. All randomized subjects will be included in the primary analysis.
 
Comparison of AQX-1125 to placebo for proportion of subjects who are responders will be used to further understand the effect of AQX-1125 on pelvic pain. P values for the test of equal numbers of responders in each group will be reported, without adjustment for multiplicity, and used descriptively.
 
Other secondary endpoints will be tested in an analogous procedure, with P values used for descriptive purposes rather than for statistical inference.
 
Safety data will be summarized with no inferential analysis planned. AEs and treatment-emergent AEs (TEAE) will be summarized by System Organ Class (SOC) and Preferred Term (PT) with counts by treatment group. Ophthalmological findings will be listed and summarized.

Date of the Synopsis: 08 March 2018

[figure not shown]

Figure 1. AQX-1125-205 study design flowchart

Table 1. AQX-1125-205 Schedule of Events

Event	Screening Period ^a		Baseline	Treatment Period			ET ^j	Safety Follow-up		
	Assessment	Visit 1	Baseline Opthal. Visit 1a	Visit 2	Visit 3	Visit 4		Off-Treatment	Telephone call ^k	Ophthalmic ^k
Week			1	6	12	NA	16	25	38	
Day (± window)	-14 (±7)	Before Visit 2	1	42 (±3)	84 (±3)	NA	112 (±3)	175 (±7)	266 (±7)	
Informed consent	✓									
Inclusion/Exclusion criteria	✓		✓							
Randomization			✓							
Demographics ^b	✓									
Medical/Surgical history	✓									
Physical examination	✓		✓		✓	✓	✓ ^m			
UPOINT classification	✓									
NIH-CPSI ^c	✓		✓	✓	✓	✓	✓			
Paper-based 11-point NRS ^{c,d}	✓		✓	✓	✓	✓	✓			
PCS ^c	✓									
PHQ-9 ^c	✓		✓	✓ ⁿ	✓ ⁿ	✓ ⁿ	✓ ⁿ			
GRA ^c				✓	✓	✓	✓			
PGI-C ^c				✓	✓	✓	✓			
IIEF, PGI-S ^c			✓	✓	✓	✓	✓			
Ophthalmic assessments ^e		✓			✓	✓	✓ ^m		✓	
12-lead supine ECG ^f	✓				✓	✓	✓ ^m			
Vital signs (HR, BP, temperature)	✓		✓	✓	✓	✓	✓			
Height	✓									
Weight	✓				✓	✓	✓			
Clinical chemistry, ^g hematology, urinalysis	✓		✓		✓	✓	✓ ^m			
Urine: bacterial culture & sensitivity, leukocyte esterase test	✓									
24-hour voiding frequency ^h			✓	✓	✓	✓	✓			
AE collection	✓		✓	✓	✓	✓	✓	✓ ¹	✓ ¹	
Concomitant medications	✓		✓	✓	✓	✓	✓			
Study drug dispensing ⁱ			✓	✓						

Event	Screening Period ^a		Baseline	Treatment Period			ET ^j	Safety Follow-up		
	Visit 1	Baseline Opthal. Visit 1a	Visit 2	Visit 3	Visit 4	Off-Treatment		Telephone call ^k	Ophthalmic ^k	
Week			1	6	12	NA	16	25	38	
Day (± window)	-14 (±7)	Before Visit 2	1	42 (±3)	84 (±3)	NA	112 (±3)	175 (±7)	266 (±7)	
Study drug compliance check				✓	✓	✓				
Study drug accountability				✓	✓	✓				
eDiary Issue/Train/Review/Collect	I/T		R	R	R	R	R/C			

Abbreviations: AE=adverse event; BCVA=best corrected visual acuity; BP=blood pressure; C=collect; ECG=electrocardiogram; eDiary=electronic diary; ET=Early Termination; GRA=Global Response Assessment; HR=heart rate; I=issue; IIEF =International Index of Erectile Function; IOP=intraocular pressure; LOCS= Lens Opacity Classification System; LogMAR=Logarithm of the Minimum Angle of Resolution; NA=not applicable; NIH-CPSI=National Institute of Health Chronic Prostatitis Syndrome Index; NRS=Numerical Rating Scale; PCS=Pain Catastrophizing Scale; PGI-C=Patient’s Global Impression of Change scale; PGI-S=Patient’s Global Impression of Severity scale; PHQ-9=Patient Health Questionnaire; R=review; T=train; UPOINT=Urinary, Psychosocial, Organ Specific, Infection, Neurologic/Systemic, Tenderness of Skeletal Muscles.

- ^a Minimum screening period is 7 days, which includes the baseline ophthalmic assessment at Visit 1a.
- ^b Demographics include age, birth year, sex, race and ethnicity.
- ^c Questionnaires must be completed prior to other assessments.
- ^d Paper-based 11-point NRS will be administered in-clinic during the study visit to assess the average and maximum daily pelvic pain.
- ^e Ophthalmic assessments include BCVA using the LogMAR chart (i.e. after manifest refraction), IOP (preferably measured by Goldmann tonometry, before and after dilation with mydriatic agent) corneal staining, slit lamp examination, and lenticular opacification using LOCS III. Baseline ophthalmology assessment can be completed as a separate visit any time during the screening period (any time before Visit 2). Background incidence of cataracts in subjects noted prior to dosing should be recorded as medical history. Ophthalmic assessments at all post-Baseline Visits should occur within the specified Visit windows.
- ^f Subjects will be resting supine for at least 5 minutes before the ECG recording.
- ^g Clinical chemistry does not need to be fasting.
- ^h Voiding frequency will be measured over a 24-hour period, within a 3-day (72 hours) window before the scheduled visits.
- ⁱ The first dose of study drug at Baseline (Visit 2) will be administered in the clinic. At subsequent Visits, subjects are to refrain from taking study drug at home on the morning of the clinic visit day and should be dosed in the clinic.
- ^j If a subject withdraws from the study, all assessments for the ET Visit should be conducted.
- ^k Subjects who withdraw from the study anytime during the study will have a follow-up period of 6 months, consisting of an Off-Treatment Safety Follow-up Visit (4 weeks post last dose), telephone call follow-up (3 months post last dose) and ophthalmic assessment (6 months post last dose).
- ^l Subjects will be asked for updates on new and ongoing (after the 28 days follow-up) ocular AEs only.
- ^m Repeat at Off-Treatment Safety Follow-up is only needed if there are outstanding safety concerns from Week 12.
- ⁿ Score will not be recorded in the database, assessment will be performed for patient safety/monitoring purposes only clinically significant findings will be reported as adverse events.

NOTE: Unscheduled visits may be conducted at any time during the study and may include the same assessments as Week 12.

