10.2 Sample Size Determination

Sample size was calculated using the 2-sample means statement in the POWER procedure in SAS. A sample size of 45 subjects per treatment group will provide 80% power to detect a 1.2-point difference in the change from Baseline maximum pelvic pain score between AQX-1125 and placebo assuming a between-subject standard deviation of 2.0 and a 2-sided 5% significance level.

Assuming a 10% rate of discontinuation from study drug, the total number of subjects to be randomized is approximately 100. Subjects who discontinue will be included in the primary analysis, resulting in a slight decrease in power if the discontinuing subjects in the placebo group have no additional change after discontinuation of study drug while the discontinuing subjects in the AQX-1125 group have a loss of efficacy after discontinuing study drug.

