2.2.2 Study Assessment Time Points

All enrolled subjects will record the maximum and average daily pelvic pain in the eDiary from Screening Visit 1 to Week 16, as well as analgesic medication taken each day. Subjects will record 24-hour voiding frequency prior to scheduled visits at baseline, Week 6, Week 12 and Week 16. Visits are scheduled at the following timepoints:

- Visit 1/Screening
- Visit 1a/ Baseline ophthalmic assessments (at any time before Visit 2)
- Visit 2/Baseline (Week 1)
- Visit 3 (Week 6)
- Visit 4 (Week 12)
- Early Termination: Subjects who withdraw from the study during the treatment period should complete an Early Termination Visit. Subjects who discontinue the double-blind treatment for any reason will be encouraged to continue with all subsequent study-related visits and a visit at Week 12 to assess efficacy endpoints.
- Off Treatment (Week 16) 4-week off drug Safety Follow-up period
- Ophthalmic Safety Follow-up Visit 6-months post last dose: Ophthalmic assessments and AE collection (ophthalmic related AEs only)
- Follow-up telephone call 3 months after the last dose: AE collection (ophthalmic related AEs only)
- Unscheduled Visits: Unscheduled visits may occur when subject needs to make a visit in between the scheduled visit dates due to an AE, difficulty complying with the study protocol requirements, or a significant change in their disease state. Unscheduled visits may be conducted at any time during the study and should include the same assessments as Week 16.

| Event | Screening Period ^a | | Baseline | Treatment Period | | ET ^j | Safety Follow-up | | |
|--|-------------------------------|----------------------------|----------|------------------|----------------|-----------------|------------------|-----------------|-----------------------------|
| | Visit 1 | Baseline Ophthal. Visit 1a | | Visit 2 | Visit 3 | | Visit 4 | Off-Treatment | Telephone call ^k |
| Week | | | 1 | 6 | 12 | NA | 16 | 25 | 38 |
| Day (± window) | -14 (±7) | Before Visit 2 | 1 | 42 (±3) | 84 (±3) | NA | 112 (±3) | 175 (±7) | 266 (±7) |
| 24-hour voiding frequency ^h | | | ✓ | ✓ | ✓ | ✓ | ✓ | | |
| AE collection | ✓ | | ✓ | ✓ | ✓ | ✓ | ✓ | ✓ ^l | ✓ ^l |
| Concomitant medications | ✓ | | ✓ | ✓ | ✓ | ✓ | ✓ | | |
| Study drug dispensing ⁱ | | | ✓ | ✓ | | | | | |
| Study drug compliance check | | | | ✓ | ✓ | ✓ | | | |
| Study drug accountability | | | | ✓ | ✓ | ✓ | | | |
| eDiary Issue/Train/Review/Collect | I/T | | R | R | R | R | R/C | | |

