2.2.15.2.6 Analysis of LOCS III

Change from baseline in LOCS III score to each scheduled visit will be summarized by treatment group. Incidence of class events (Class I, Class II and Class III) will be summarized. Incidence of cumulative events (at least a Class I event, at least a Class II event and a Class III event) will be summarized and p-values will be provided for descriptive purposes, using a chi-square test. The definition of class I, II and III events are described in the Rosiptor Ophthalmology Manual.

The LOCS III grading system values will also be analyzed by means of a longitudinal MMRM model which accounts for the between-eye correlation. The details of this MMRM is provided in Appendix C – LOC III Grading System MMRM Analysis.

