2.2.15.3 Laboratory Data

Shift tables will be presented showing the shift in (Normal/Low/High) from baseline to Week 12, off treatment follow-up and early termination visit by treatment group.

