2.2.15.4 Vital Signs, 12-Lead ECG, physical examination and Other Observations Related to Safety

Vital signs include blood pressure and heart rate. Actual values and change from baseline will be tabulated by treatment group at baseline and each post-baseline.

Shift tables will be provided for ECG data (Normal/Abnormal) from Screening Visit to Week 12, off treatment follow-up and early termination visit by treatment group.

Physical Examination Findings will be presented in the listings but not tabulated.

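### Transient mid-treatment lab, ECG, IOP, corneal and slit lamp abnormalities that are not judged clinically significant reach no by-arm table, because the SAP ties its tables to named visits and has no rule for unscheduled results

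*Protocol*

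**What the plan says.** **Schedule.** In protocol Table 1, labs are at Visits 1, 2 and 4 and ECG at Visits 1 and 4. Eye exams are at Visit 1a, Visit 4 and the 6-month follow-up. All three are also done at early termination (ET), and at Week 16 only if safety concerns remain from Week 12. Visit 3 (Week 6) has none of them, and the Visit 3 list in protocol 9.4.3.1 agrees.

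**Unscheduled visits.** The note to protocol Table 1 says: "Unscheduled visits may be conducted at any time during the study and may include the same assessments as Week 12". Protocol 9.4.5.4 and the note to the SAP's own schedule say the same. SAP 2.2.2 says: "Unscheduled visits may be conducted at any time during the study and should include the same assessments as Week 16". It gives three possible reasons for such a visit: an AE, trouble complying with the protocol, or a significant change in disease state.

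**Analysis.** SAP 2.2.15.3 plans lab tables "showing the shift in (Normal/Low/High) from baseline to Week 12, off treatment follow-up and early termination visit". SAP 2.2.15.4 says: "Shift tables will be provided for ECG data (Normal/Abnormal) from Screening Visit to Week 12, off treatment follow-up and early termination visit". SAP 2.2.15.2.5 summarises LOCS III, visual acuity (BCVA) and IOP at Baseline, Week 12, Week 16, 6 months and ET, and corneal staining and slit lamp at Baseline, Week 12 and 6 months. SAP 2.2.15.2.6 adds: "Change from baseline in LOCS III score to each scheduled visit will be summarized by treatment group".

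**Routes not tied to a visit.** Clinically significant lab, ECG and ocular findings are recorded as AEs (protocol 9.3.2 to 9.3.4), and TEAEs are tabulated by arm (SAP 2.2.15.2). Class II/III LOCS III shifts are derived by program, and they and a BCVA loss of 2 or more lines count as TEAESIs, also tabulated by arm (SAP 2.2.15.2.4). All data are listed (SAP 2.1).

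**The concern.** A shift table shows movement out of range without depending on an investigator's view of clinical significance. Here the lab and ECG shift tables are the only by-arm analysis of those values in the SAP's safety sections, although protocol 10.4.3 also promised change-from-baseline summaries. A man who completes treatment has one scheduled on-drug lab and ECG, at Day 84 (±3). If a value moves out of range at Week 5, is seen at an unscheduled visit and is normal again at Week 12, the shift table records him as normal.

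SAP 2.2.11 plans no safety monitoring committee, so the final tables carry most of the weight in comparing the arms. What is at stake is the completeness of the descriptive safety comparison. The primary efficacy test is not affected.

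**Working it through.** **1. Men per arm.** The sample size section states: "A sample size of 45 subjects per treatment group will provide 80% power to detect a 1.2-point difference", "assuming a between-subject standard deviation of 2.0 and a 2-sided 5% significance level". With a noncentral t, the noncentrality is 1.2 / (2.0 × √(2/45)) = 2.85 on 88 df, which gives power of 80.4% (79.5% at 44 per arm), so the stated figure reproduces. For discontinuation, 90 / (1 − 0.10) = 100, or about 50 per arm. The point below uses only that 50.

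**2. Gap in the schedule.** Visit 2 (Day 1) comes before the first dose and the next scheduled lab, ECG and eye exam are at Day 84: 84 − 1 = 83 days with none.

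**3. Where an unscheduled result can go.**

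| Measure | Visits in the SAP value tables | By-arm route not tied to a visit |
|---|---|---|
| Labs | Week 12, off-treatment, ET | TEAE if clinically significant |
| ECG | Week 12, off-treatment, ET | TEAE if clinically significant |
| LOCS III | Change: scheduled visits | Class-event incidence and Class II/III TEAESI; no visit limit stated |
| BCVA | Week 12, Week 16, 6 months, ET | TEAESI if loss of 2 or more lines; otherwise TEAE if clinically significant |
| IOP | Week 12, Week 16, 6 months, ET | AE if clinically significant; no numeric TEAESI criterion |
| Corneal staining, slit lamp | Week 12, 6 months | AE if clinically significant; no numeric TEAESI criterion |

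**4. Tracing one result.** Take a lab value that is abnormal at an unscheduled visit in Week 5 and normal at Week 12.
- Judged clinically significant: 0 in the Week 12 shift column, 1 subject in the TEAE table.
- Not so judged: 0 in the shift column, 0 in the TEAE table, present in the listing.

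The same holds for ECG, and for an IOP, corneal or slit lamp finding that meets no TEAESI criterion. A Class II LOCS III shift or a 2-line BCVA loss at the same visit meets a TEAESI criterion, and no visit limit is stated.

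**5. Size, on assumed rates.** The documents give no rate of unscheduled testing or of transient abnormality. If 2%, 5% or 10% of 50 men per arm had one, that is 50 × 0.02 = 1, 50 × 0.05 = 2.5 or 50 × 0.10 = 5 men. These are ceilings on what is lost: they require every case to be found at an unscheduled test, to be normal by Week 12 and not to be judged significant. In that extreme the Week 12 column reads 0/50. The two-sided 95% upper limit is 1 − 0.025^(1/50) = 7.1%, below the assumed 10%.

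**6. Content of the visit.** Three places (protocol Table 1 note, protocol 9.4.5.4, SAP schedule note) say such a visit *may* carry the Week 12 set, which includes labs, ECG and eye exams. SAP 2.2.2 says it *should* carry the Week 16 set, where these depend on concerns left over from Week 12. Before Week 12 that condition cannot be met, so on this reading an unscheduled visit in Week 5 calls for none of them.

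**The case against.** A reader might infer that any mid-treatment abnormality resolved by Week 12 counts as zero in the safety comparison. The documents do not support that. Clinically significant findings enter the TEAE tables from first dose to 28 days after last dose, whatever the visit and whether or not they resolve.

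Nor are lens and acuity findings lost: Class II/III shifts are derived against fixed cut-offs, a 2-line BCVA loss is a TEAESI, and class-event incidence carries no visit limit. Only the LOCS III change-from-baseline sentence is confined to scheduled visits.

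A reader might also infer that unscheduled visits are AE-driven and so hold the results most likely to be abnormal. An AE is one of three stated reasons, and no figure supports the rest.

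It is fair to add that no sentence says unscheduled results are dropped. That stands as a caution, but the visit lists are explicit. Where the SAP wants an off-schedule LOCS III value used, it writes a rule: Appendix C assigns ET values to the next scheduled visit. Nothing comparable exists for unscheduled results. Protocol 9.3.4 lets out-of-range labs be repeated, and the SAP does not say which value fills the column.

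Finally, safety is descriptive in a trial of about 100 men, and event-driven tests may be unequal between arms. Both are true. The second is a reason to show the number tested, not to omit the values. The Week 16 reading would also mean fewer mid-treatment results to omit, which is a further reason to settle it.

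**Conclusion.** The gap is real and narrow. As written, a transient lab, ECG, IOP, corneal staining or slit lamp abnormality that is not judged clinically significant and meets no TEAESI criterion reaches no by-arm table. This rests on reading the SAP's visit lists as complete, in the absence of a mapping rule or a worst-post-baseline summary.

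Its frequency cannot be known from the documents; the 1 to 5 men per arm is an illustration on assumed rates. The conflict over the content of an unscheduled visit is plain on the face of the text. Sample size, power and alpha are unaffected. This is a cheap improvement worth making before unblinding, not a defect that undermines the trial.

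**What to change.** - **SAP 2.2.15.3 and 2.2.15.4:** add to the lab and ECG shift tables a by-arm column for the worst post-baseline value from first dose to 28 days after last dose, using scheduled, repeat and unscheduled results. State how an off-treatment visit later than 28 days is treated; Day 112 + 3 is 31 days after a last dose on Day 84.
- **SAP 2.2.15.2.5:** add a by-arm worst-change count for IOP, and a count of men with any post-baseline abnormality for corneal staining and slit lamp.
- **All of these:** show by arm the number of men tested at unscheduled visits.
- **SAP 2.2.15.2.4 and 2.2.15.2.6:** state that TEAESI derivations and LOCS III class-event counts use unscheduled exams.
- **Named-visit columns:** state which result is used when a test was repeated.
- **Visit content:** reconcile SAP 2.2.2 with the protocol Table 1 note, protocol 9.4.5.4 and the SAP schedule note.

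The cost is SAP wording and a few table columns, with no new data. The downside is that worst-value counts rise with the number of tests, so an arm with more event-driven visits can look worse for that reason alone. The numbers tested let a reader judge this.
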